(2) Risk of breach in confidentiality/privacy: All hard copy data will be stored in locked offices at MMC and MGUH ID Clinics. Computerized data will be protected by maintaining the data that links study number to high level identifiers (e.g. full name, medical record number) in a single, secure file at both clinic locations. Study computers will be password protected and secured behind the respective institutional firewalls. Data transit between the PSFW+ application server and database or other data stores will be secured via SSL. Data from the PSFW+ application database will be transferred to Legacy's local servers via direct SSL connection with the database and stored on secure servers with restricted access rights. Data from the Vanilla Forums community software will be transferred to Legacy's local servers via SFTP ("Secure File Transfer Protocol" or "FTP over SSL"). Data from the ACASI uploads, i.e. participants' questionnaire responses, will be transferred to the AECOM EISMU via secure Sharepoint connection. The system interoperates with email to distribute alerts and notifications, and audits all editing and updating of information on the site. In addition, the collaborative portals host and integrate with Citrix XenApp as an application delivery system which provides end-users with a fully encrypted session. Security arrangements for data maintained by the EISMU are detailed in the Protection of Study Data section above. If by any chance the security of the databases is compromised, study data will be numerically coded and useless to someone without a data dictionary. Prior to data transfer to the biostatistician for analysis, personally identifying information will be removed from data tables. The study staff will apply to the appropriate parties for a Certificate of Confidentiality to protect subjects supplying study data pertaining to illicit substance use and sexual preference. There are also privacy risks related to participating in an online social network. The study team has sought advice and counsel from HIV specialists, technology specialists, PLWH, and numerous lawyers before creating the PSFW+ Terms of Use and Privacy Policy. Registration on the site requires accepting the conditions spelled out in each of these documents which appear next to the "Submit" button on the registration page as well as in the header of all content pages. Both documents emphasize that anything a user posts in the community should be considered public information, and that others may assume that they have HIV/AIDS based on personal information they post on the website since it is a quit smoking website for smokers living with HIV.

(3) Emotional distress: Both ID Clinics offer on-site mental health support services and are situated in close proximity to their respective psychiatric emergency departments. Study subjects that indicate at any time in-person, on the phone, or in the community that they are experiencing distress (esp. worsening of depression and/or anxiety) will be advised how to avail themselves of appropriate emergency clinical services if the need should arise. In addition, subjects scoring out of range on the depression and/or anxiety indices included in the study questionnaires will be contacted by study staff and offered referral to mental health services. Drs. [name] and [name] will monitor and strictly adhere to adverse events reporting procedures within their clinics and IRBs. A data safety monitoring officer will oversee the data safety monitoring plan. [name] will conduct weekly supervision meetings with the PSFW+ Community Administrator, [name], to discuss any issues that arise in the community that may be of concern. [name] will alert [name] immediately if a participant posts content in the community that indicates the potential for harm or adverse event. [name] will attempt to contact the participant using the phone number s/he provided during site registration to assess the potential for harm and refer to the emergency services protocol at each clinic. If the participant cannot be reached, [name] will contact hospital administration to activate the hospital's protocol for contacting patients about urgent matters when they are not reachable by phone. Each hospital will follow its respective protocol for calls to the patient's emergency contacts and/or dispatching police to locate the patient.

(4) Nicotine replacement therapy side effects: The risks of serious adverse effects of nicotine replacement therapy are small, and its potential health benefits far outweigh its risks. Subjects will be encouraged to review the drug information provided with the product and to report adverse effects to their clinic providers. Study candidates with contraindications to NRT or whose providers deem to be at unacceptable risk from NRT will be excluded from the study.

Adverse Event Response and Reporting

The MMC ID Clinic has primary care providers on-site Monday through Friday from 9am-5pm. During off hours, patients may contact covering attending physicians by [contact] through an emergency beeper system. For emotional/psychological issues, the ID Clinic has an on-site mental health team consisting of two psychiatrists, a psychologist, and a social work therapist. During off-hours, the MMC psychiatric emergency department is located in an adjoining area of the hospital. The Georgetown Division of Infectious Diseases has an ID Fellow on call for emergency issues 24/7/365 who is able to reach [name]. All study enrollees will be given the 24 hour number for the participant to call in the event of an urgent or emergent issue. Additionally the Division has access to the Department of Psychiatry with 24 hour coverage through the Emergency Department which is located in the MedStar Georgetown University Hospital on the University campus. For outpatient follow-up, the Department of Psychiatry utilizes psychiatrists, psychologists and licensed clinical social workers based on the needs of the subject.

5.C. POTENTIAL BENEFITS OF THE PROPOSED RESEARCH TO HUMAN SUBJECTS AND OTHERS

Subjects may benefit from participation in this research in several ways. By participating in a smoking cessation treatment program, subjects may increase the likelihood that they will attempt to quit smoking and be successful. Additionally, participants will gain a greater understanding of their smoking behavior that may help them to quit successfully in the future. Finally, although this is not a direct benefit, all participants will be involved in a project to evaluate innovative treatments for smoking cessation in this highly vulnerable population that may ultimately produce an enormous public health impact. If proven effective, PSFW+ could be promoted at HIV care sites throughout the country as a broad-reach intervention that addresses an important health disparity. The belief that the benefits of smoking cessation interventions outweigh their risks is an accepted principle of medical practice. The only additional risks to study subjects in the proposed project are the risks of breach of patient privacy and emotional distress related to the data collection process. The investigators believe that these small risks are outweighed by the potential benefits of the study.

5.D. IMPORTANCE OF THE KNOWLEDGE TO BE GAINED

Cigarette smoking continues to be a major preventable cause of death in the United States, and improvements in treatment options are needed specifically for PLWH. The scope of the problem of smoking in PLWH and the limits of knowledge related to smoking cessation in PLWH are highlighted in **Section 3.A**. The Internet has the potential to deliver a low-cost and effective cessation intervention to PLWH smokers throughout the US. Usage data and satisfaction survey responses may also be useful in planning future studies and optimizing future web interventions.

5.E. DATA AND SAFETY MONITORING PLAN

All aspects of the data safety monitoring plan will be reviewed and approved by the governing IRB prior to study initiation. Drs. [name] and [name] will be responsible for monitoring the safety and efficacy of this minimal risk study, executing the data and safety monitoring plan, and reporting the findings annually to the NIH. A Data Safety Monitoring Officer (DSMO) will be designated at Montefiore. S/he will be a physician without direct clinical responsibilities in the MMC ID Clinic, and without conflicts of interest relating to the proposed study. Parameters to be tracked, at least quarterly, will include subjects' sociodemographic characteristics, expected versus actual accrual statistics, study attrition, serious adverse events, and protocol amendments. The DSMO will receive a summary statement containing these data quarterly.

Mechanisms in place to protect patient privacy are detailed in **Section 5.B.** Additionally, study staff will apply to the appropriate authorities for a Certificate of Confidentiality to protect subjects supplying study data pertaining to illicit substance use and sexual orientation.

Serious adverse events (SAEs) will be defined as death, hospitalization, or immediately life-threatening illness (including mental illness). SAEs will be reported to the clinical site's IRB within 72 hours of study personnel becoming aware of them. The relationship of each SAE to study participation will be graded by the study staff as unrelated, probably not related, possibly related, probably related, or definitely related. Provisions for responding to psychiatric SAEs have been previously detailed (see **Section 5.B.**). For each SAE the DSMO, PI, and the IRB will consider whether the risk benefit ratio of the study has been altered necessitating study discontinuation, modification of the informed consent document, and/or notification of current study subjects. The site PI will notify the NIH of each SAE that occurs within 72 hours of awareness and will file a full SAE report for each event once clinical information becomes available.

5.F. REQUIRED EDUCATION IN THE PROTECTION OF HUMAN RESEARCH PARTICIPANTS

All members of the investigative staff have completed formal training programs in the protection of human research participants and will maintain current certification throughout the course of the trial. Documentation of program completion will be supplied to the NIH prior to project initiation.

LITERATURE CITED

1. Antiretroviral Therapy Cohort C. Causes of death in HIV-1-infected patients treated with antiretroviral therapy, 1996-2006: collaborative analysis of 13 HIV cohort studies. *Clinical infectious diseases : an official publication of the Infectious Diseases Society of America*. 2010;50(10):1387-96. doi: 10.1086/652283. PubMed PMID: 20380565; PMCID: 3157754.

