Social Cognitive Theory,⁹³ content focuses on providing information, increasing motivation to quit, and increasing self-efficacy to resist smoking temptations (**Table 2**) via presentation of objective data as well as hypothetical “real world” scenarios of particular relevance to PLWH smokers. Users are given tools and options to cope with smoking urges. NRT use is encouraged. **Online social network:** The PSFW+ community runs on open source forum software by Vanilla Forums. We created a full-featured discussion forum with unlimited categories and user profiles that is customized to look like the main site. Vanilla Forums enables single sign-on for a seamless experience between the static content and online community. PSFW+ users can create a user profile with a unique avatar or personal photo, and can create a profile “wall” on which other users may post comments, images, or video. The primary interface is a feed of discussion threads: users create discussions or polls, and other users may post comments to the discussion or answer the poll. Users can also exchange private messages. The **PSFW+ Community Guidelines** emphasize the importance of creating and maintaining a safe environment for people to exchange information and support. The guidelines also remind users that all content posted in the community is publicly available, and that the administrator may remove messages that are spam or solicitations. Users who persistently violate Community Guidelines will have their community profile removed from the site. Our experience with several online communities with thousands of users is that these occurrences are infrequent; should they occur during the study period, we will account for this in our analyses. Involvement of an experienced administrator is integral to managing these situations proactively to ensure the smooth operation and success of an online community,^{24,94} especially during its nascent phase. The **PSFW+ Community Administrator** will monitor all public discussions and comments on the community, encourage interactions between community members, review all reports of inappropriate content that do not follow the Community Guidelines (such as spam), and serve as the main liaison between technical staff and community members for any technical issues. The **PSFW+ Terms of Use** and **Privacy Policy** make explicit that all content posted in the community is publicly available information and users are legally responsible for any content they post on the site. The registration page states “By clicking Submit, I agree to the Positively Smoke Free Terms of Use and Privacy Policy” (available via hyperlink). The treatment of the unique privacy concerns of a PLWH online community and its attendant legal implications have been carefully considered and are discussed in detail in the Human Subjects section.

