1. Describe rates of and duration of tobacco abstinence, and identify clinical and demographic factors associated with maintenance of abstinence, among participants of the parent study.
2. Identify associations between smoking status and COVID-19 related outcomes and healthcare utilization among participants of the parent study.
3. Identify associations between smoking status on HIV-related outcomes and healthcare utilization among participants of the parent study.

Methods

This will be a prospective study of participants in the trial: *Randomized Controlled Trial of An Internet Cessation Program Plus Online Social Network for HIV + Smokers*. The trial was conducted at two sites, Montefiore Medical Center and Johns Hopkins University Hospital. Only the participants from the Montefiore site will be invited to join the follow-up study proposed in this amendment. For the sake of the amendment, “participants” refers to participants at Montefiore. All prior participants in the study are eligible for this proposed follow-up study. Study personnel will contact prior participants via telephone to offer participation in the follow-up study.

The first component of the follow-up study will include a 15-20 minute IRB-approved telephone interview with questions related to: current smoking status; smoking quit attempts; motivation to quit; alcohol and drug use; COVID-19 illness, management, vaccination status, and attitudes toward vaccination; overall healthcare utilization over the prior year including visits with an HIV provider, emergency department visits, and hospitalizations; and questions related to perceptions of HIV care.

Participants who report tobacco abstinence during the telephone interview will be invited for an in-person visit to measure exhaled carbon monoxide and to submit a cheek swab for biobanking for future genetic research. Both of these are painless, essentially risk-free procedures.

Data Security:

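### The plan gives no systematic, arm-neutral way to find SAEs, and one detection route exists only in PSFW+, so SAE counts may be incomplete and any tabulation by arm is open to detection bias.

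*Combined protocol and SAP*

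**What the plan says.** Section 5.E (Data and Safety Monitoring Plan) states: "Serious adverse events (SAEs) will be defined as death, hospitalization, or immediately life-threatening illness (including mental illness". The clinical site's IRB is told "within 72 hours of study personnel becoming aware of them". Each event is graded for relation to the study, and the DSMO, PI and IRB consider whether the risk-benefit ratio has changed. SAEs are among the parameters tracked at least quarterly, and "The DSMO will receive a summary statement containing these data quarterly".

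Section 3.C.5 lists the measures for baseline and the 1-, 3- and 6-month assessments. The safety-related items are NRT side effects and the depression and anxiety scales. No item asks about hospital admission or serious illness.

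Section 3.C.4.e gives PSFW+ a Community Administrator who "will monitor all public discussions and comments on the community". Section 5.B has posts that suggest harm or an adverse event escalated at once. The control site has no dedicated community. Section 5.B also asks participants "to report adverse effects to their clinic providers".

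**The concern.** Defining SAEs and setting a reporting clock does not find them. If no one asks, an admission to another hospital between visits reaches the study only if the participant mentions it or clinic staff happen to pass it on. An event that is not found cannot enter the case-by-case review of risk and benefit in Section 5.E.

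The second issue is symmetry. One route to awareness is built into one arm and absent from the other. If SAEs are ever shown by arm, part of a difference could reflect who was being watched. The 2021 amendment shows that the question is easy to ask: its telephone survey covers "overall healthcare utilization over the prior year including visits with an HIV provider, emergency department visits, and hospitalizations". That survey was proposed after the trial had closed, covers one site only, and asks about the prior year as healthcare utilization, so it does not fill the gap.

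**Working it through.** The plan states no SAE rate, SAE sample size or SAE test, so there is no figure to reproduce. The check has two parts.

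**1. Routes by which staff could learn of an SAE**

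| Route | PSFW+ | Control | Section |
|---|---|---|---|
| Assessments at 1, 3 and 6 months | yes | yes | 3.C.5 |
| NRT side-effect items | yes | yes | 3.C.5 |
| Staff contact after an out-of-range depression or anxiety score | yes | yes | 5.B |
| Care at a study clinic, with study staff on site full-time | yes | yes | 3.C.4.b, 3.C.4.c |
| Off-hours physician cover; 24-hour number (Georgetown description) | yes | yes | 5.B |
| Staff call after 10 days of non-use | yes | yes, same trigger | 3.C.4.e |
| Administrator reads public posts and escalates | yes | no | 3.C.4.e, 5.B |
| Structured hospitalization or SAE question | none | none | not listed |
| Records check, or rule for providers to inform study staff | none | none | not stated |

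The gap in ascertainment affects both arms. The difference between arms rests on one row, community monitoring.

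**2. Illustration of size**

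From the documents: n = 275 per arm (3.C.6.e). Assumed, because the documents give no values:
- true 6-month SAE risk p = 5-20%, equal in both arms;
- capture through shared routes c = 50-90%;
- share e = 5-25% of otherwise missed events found through the community.

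Formulas:
- Expected recorded, control = n × p × c
- Expected recorded, PSFW+ = n × p × [c + (1 − c) × e]
- Apparent ratio = 1 + e × (1 − c)/c, which does not depend on p

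At p = 10% the true expectation is 275 × 0.10 = 27.5 per arm:

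| c | e | Control | PSFW+ | Ratio |
|---|---|---|---|---|
| 0.90 | 0.05 | 24.75 | 24.89 | 1 + 0.05 × 0.10/0.90 = 1.006 |
| 0.70 | 0.10 | 19.25 | 20.08 | 1 + 0.10 × 0.30/0.70 = 1.043 |
| 0.50 | 0.25 | 13.75 | 17.19 | 1 + 0.25 × 0.50/0.50 = 1.250 |

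The ratio therefore runs from about 1.01 to 1.25. By assumption, the control arm misses 10-50% of events.

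If someone tested the two arms at two-sided 0.05, the chance of a spurious PSFW+ excess would run from 2.6% to 15.1%, against a nominal 2.5% in that direction. The top value is at p = 20%, c = 0.50, e = 0.25, where 55 × 0.50 = 27.5 events are expected in control and 55 × 0.625 = 34.4 in PSFW+. When e is 10% or less, the chance is at most 5.7%.

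**The case against.** The strongest reply is that the 72-hour phrase is a reporting deadline and does not limit which SAEs count, that nearly every route is shared, and that no by-arm SAE comparison is planned in 3.C.6 or 5.E. The investigators are also bound by clinic and IRB adverse-event procedures that the document does not reproduce, and 5.E calls this a minimal risk study. All of this is right, and it limits the point to incomplete ascertainment plus one asymmetric route. It does not supply the missing question.

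A reader might infer more than the documents support:

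- **That the 10-day call makes detection unequal.** Its trigger is deliberately matched. It differs by arm only if recorded non-use differs. Control use is seen mainly through portal logins, so this is possible, but nothing shows it.
- **That staff contact ends at 7-8 weeks.** The 8-week limit in 3.C.4.e applies to weekly messages to active users. No end date is given for calls or community monitoring.
- **That NRT effects never reach the study.** Participants are told to "report adverse effects to their clinic providers", but 3.C.5 also assesses NRT side effects directly. What is missing is a stated relay for serious events.
- **That the bias must be large.** At 50% shared capture the ratio is 1 + e, so exceeding 1.25 would need public posts to reveal more than a quarter of the events that all other routes miss. Posts are more likely to reveal distress than medical admissions.

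**Conclusion.** The point holds in a limited form. The plan makes every hospitalization an SAE but lists no systematic way to learn of one, so the counts sent to the DSMO may be incomplete. Community monitoring adds a route in PSFW+ only, so any tabulation by arm is open to detection bias, probably toward more recorded events in PSFW+ and mainly for psychiatric or distress events.

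The size is unknown. The range of 1.01 to 1.25 rests wholly on assumed risk and capture rates, and the effect is small when shared routes find most events. A reader might conclude that the counts are certain to be low or that the arms cannot be compared at all. The documents give no rates to show the first, and the mostly shared routes argue against the second. The primary abstinence analysis is not affected. This is an inexpensive improvement to safety ascertainment.

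**What to change.** - Add one question, worded identically in both arms, at the 1-, 3- and 6-month assessments, in person or by telephone: since the last assessment, has the participant been admitted to hospital or had a life-threatening illness, including mental illness? Staff review the answer on the day, so that a yes starts the existing 72-hour clock.
- State the SAE window as randomization to the 6-month visit.
- Record on the SAE form how each event was found: scheduled question, call, community post, clinic provider or other.
- Report all SAEs by arm and by source, and show events found only through the community separately. Do not restrict the display to events found by the question, because self-report misses deaths and participants who miss visits.

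The cost is one item at assessments already held, same-day review of the answers, and one field on a form. The downside is more unrelated hospitalizations to report. The amendment says that the parent trial closed in 2020, so the question cannot be added to it retrospectively. What can still be done there is to report by arm and source where the source can be recovered, with a plain statement of how SAEs were found.

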151. van Uden-Kraan CF, Drossaert CH, Taal E, Seydel ER, van de Laar MA. Self-reported differences in empowerment between lurkers and posters in online patient support groups. *Journal of medical Internet research*. 2008;10(2):e18. Epub 2008/07/26. doi: 10.2196/jmir.992. PubMed PMID: 18653442; PMCID: 2483925.

Amendment for *Randomized Controlled Trial of An Internet Cessation Program Plus Online Social Network for HIV + Smokers* (IRB# 2015-4723)

Amendment Date: 10-4-21

Overview of the proposed amendment

This amendment is being submitted to expand the scope of the previously approved study. The specific changes sought by this amendment include:

- 1) Inviting participants previously enrolled in the parent study to participate in a new telephone survey.
- 2) Inviting those participants reporting abstinence from cigarette smoking during the telephone survey to participate in an in-person study visit to measure exhaled carbon monoxide and undergo a cheek swab for biobanking.

Background for the amendment

The parent study of this amendment, a *Randomized Controlled Trial of An Internet Cessation Program Plus Online Social Network for HIV + Smokers*, was closed in 2020 and represents the first randomized controlled trial of tobacco treatment to report abstinence efficacy at the 6-month timepoint among people with HIV (PWH) smoker in the US¹. This well characterized cohort of study participants represents an important population for understanding predictors of long-term smoking cessation. Additionally, this population represents an opportunity to elucidate associations between smoking cessation and healthcare utilization, outcomes related the COVID-19 and vaccination for COVID-19, and HIV care.

Ref:

¹Stanton CA GA, Kim RS, Chander G, [name] J. Multicenter RCT of a web-based cessation program plus online social network for HIV+ smokers. Presented at the Society for Research on Nicotine & Tobacco 2021 annual meeting, Feb. 24-27, 2021.

Objectives

The objectives of the study proposed in the amendment are to:

1. Describe rates of and duration of tobacco abstinence, and identify clinical and demographic factors associated with maintenance of abstinence, among participants of the parent study.
2. Identify associations between smoking status and COVID-19 related outcomes and healthcare utilization among participants of the parent study.
3. Identify associations between smoking status on HIV-related outcomes and healthcare utilization among participants of the parent study.

Methods

This will be a prospective study of participants in the trial: *Randomized Controlled Trial of An Internet Cessation Program Plus Online Social Network for HIV + Smokers*. The trial was conducted at two sites, Montefiore Medical Center and Johns Hopkins University Hospital. Only the participants from the Montefiore site will be invited to join the follow-up study proposed in this amendment. For the sake of the amendment, “participants” refers to participants at Montefiore. All prior participants in the study are eligible for this proposed follow-up study. Study personnel will contact prior participants via telephone to offer participation in the follow-up study.

The first component of the follow-up study will include a 15-20 minute IRB-approved telephone interview with questions related to: current smoking status; smoking quit attempts; motivation to quit; alcohol and drug use; COVID-19 illness, management, vaccination status, and attitudes toward vaccination; overall healthcare utilization over the prior year including visits with an HIV provider, emergency department visits, and hospitalizations; and questions related to perceptions of HIV care.

Participants who report tobacco abstinence during the telephone interview will be invited for an in-person visit to measure exhaled carbon monoxide and to submit a cheek swab for biobanking for future genetic research. Both of these are painless, essentially risk-free procedures.

Data Security:

Data will be collected and stored using a secure, password protected database accessible only to authorized study personnel. Data will be de-identified and all participants will be assigned a unique identifier. A file linking identifying information to unique identifiers will be kept separately from the data itself and will be stored in a locked file cabinet within a locked office, only accessible to authorized study personnel. Upon completion of the analysis, the documents linking the identifiable data to unique study identifiers will be destroyed.

Data Analysis:

Participants achieving tobacco abstinence will be compared to those not achieving abstinence according to clinical characteristics, sociodemographic characteristics, and interview responses. Using standard bivariate and multivariate methods, we will identify factors associated with tobacco abstinence, healthcare utilization, COVID-19 related outcomes and interview responses, and HIV-related outcomes and interview responses.

Informed Consent

All participants will undergo the process of informed consent prior to enrollment in this follow- up study. For participants in the telephone interview component, verbal informed consent using an IRB-approved script will be obtained. For participants in the in-person visit component, signed informed consent using an IRB-approved document will be obtained. Participants agreeing to the cheek swab for biobanking of genetic material for future research will also provide signed informed consent for that specific procedure.

Reimbursement:

Participants who consent to and complete the telephone interview will be reimbursed \$20 for their time. Participants completing the in-person study visit will be reimbursed an additional \$50. Participants participating in the in-person study visit will also be reimbursed for a \$6 Metrocard for roundtrip travel to the study site.

Risks/Benefits/Alternatives:

For participants of the telephone interview and in-person study visit, the primary risk will be loss of confidentiality. This risk is mitigated by the data security procedures described above. Participants may also feel uncomfortable with certain questions. If this occurs, participants can choose to end their participation at any time. For participants of the in-person study visit, the measurement of exhaled carbon monoxide is non-invasive and the cheek swab is minimally invasive, both with virtually no risk. Participants may choose to end their participation at any time during the study.

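### The 2021 follow-up amendment relates smoking status at the interview to COVID-19 illness and hospital use before it, with no time ordering, so illness-prompted quitting can bias those associations

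*Combined protocol and SAP*

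**What the plan says.** All references are to the amendment dated 10-4-21 unless stated otherwise.

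- **Design label (Methods).** "This will be a prospective study of participants in the trial".
- **Exposure (Methods).** The telephone interview has "questions related to: current smoking status; smoking quit attempts; motivation to quit; alcohol and drug use". Smoking status is therefore status at the call.
- **Outcomes (Methods).** The same interview covers "COVID-19 illness, management, vaccination status, and attitudes toward vaccination", with no look-back limit or dates stated. It also covers "overall healthcare utilization over the prior year including visits with an HIV provider, emergency department visits, and hospitalizations".
- **Objective 2.** "Identify associations between smoking status and COVID-19 related outcomes and healthcare utilization among participants of the parent study".
- **Objective 3.** "Identify associations between smoking status on HIV-related outcomes and healthcare utilization among participants of the parent study". The source and timing of the HIV-related outcomes are not given.
- **Analysis (Data Analysis).** "Participants achieving tobacco abstinence will be compared to those not achieving abstinence according to clinical characteristics, sociodemographic characteristics, and interview responses". By bivariate and multivariate methods, "we will identify factors associated with tobacco abstinence, healthcare utilization, COVID-19 related outcomes" and other interview responses.

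Participants who report abstinence are also invited to a visit for exhaled carbon monoxide and a cheek swab. No follow-up for later outcomes is described. Objective 1 includes the duration of abstinence, but neither objective 2 or 3 nor the Data Analysis paragraph uses duration or a quit date. The parent protocol (3.C.5) verifies 7-day abstinence at 1, 3 and 6 months. The amendment does not name that status as an exposure.

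**The concern.** COVID-19 illness and the past year's emergency visits and hospitalisations have already happened when smoking status is recorded. An illness can itself lead a smoker to quit. That person then enters the abstinent group and brings the event along. Covariate adjustment does not repair this, because the outcome may have changed the exposure.

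The amendment's background presents the cohort as a chance to learn how smoking cessation relates to healthcare use, COVID-19 outcomes and HIV care. Readers will take the results as bearing on the benefit of quitting. Illness-prompted quitting pushes the odds ratio for abstinent versus smoking participants upwards, so a real benefit could be hidden or abstinence could look harmful.

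**Working it through.** The amendment states no sample size, effect size or event rate, so there is no planned figure to reproduce. The check is an expected 2x2 table with hospitalisation as the event. It shows direction and possible size only.

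**Inputs (all assumptions)**
- a = share abstinent at the start of the one-year window: 0.10 or 0.20
- h = risk of hospitalisation in smokers: 0.20
- true odds ratio (OR), abstinent versus smoking at the start: 1.0 or 0.6
- b = probability that a smoker without the event quits before the call: 0.05
- r = probability that a hospitalised smoker quits before the call: 0.05, 0.10 or 0.20

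**Risk in those abstinent at the start**

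odds = OR × h/(1−h). For OR 0.6: 0.6 × 0.25 = 0.15, so the risk is hA = 0.15/1.15 = 0.1304.

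**Cells by status at the interview**
- abstinent, event: AE = a·hA + (1−a)·h·r
- abstinent, no event: AN = a·(1−hA) + (1−a)·(1−h)·b
- smoking, event: SE = (1−a)·h·(1−r)
- smoking, no event: SN = (1−a)·(1−h)·(1−b)
- apparent OR = (AE × SN)/(AN × SE)

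**One case in full: a = 0.10, true OR 0.6, r = 0.20**
- AE = 0.01304 + 0.03600 = 0.04904
- AN = 0.08696 + 0.03600 = 0.12296
- SE = 0.90 × 0.20 × 0.80 = 0.14400
- SN = 0.90 × 0.80 × 0.95 = 0.68400
- apparent OR = (0.04904 × 0.684)/(0.12296 × 0.144) = 1.89

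**All cases**

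| True OR | a | r = 0.05 | r = 0.10 | r = 0.20 |
|---|---|---|---|---|
| 1.0 | 0.10 | 1.00 | 1.38 | 2.29 |
| 1.0 | 0.20 | 1.00 | 1.23 | 1.78 |
| 0.6 | 0.10 | 0.72 | 1.07 | 1.89 |
| 0.6 | 0.20 | 0.66 | 0.86 | 1.34 |

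**Where the sign changes.** Setting AE × SN = AN × SE with true OR 0.6 and solving for r gives 9.1% (a = 0.10) and 13.1% (a = 0.20).

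**Other inputs.** Borrow the parent trial's design abstinence rates (7.5% and 15.4%, section 3.C.6.e) as the range for a, let h run from 10% to 30%, and keep b at 5%. A true OR of 0.7 then passes 1 once 7.2% to 9.8% of smokers with an event quit. A true OR of 0.5 passes 1 at 8.7% to 13.4%.

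**With status fixed at the start of the window.** Later quitting cannot move anyone between groups, so the model returns the true OR. This holds by construction and ignores confounding and recall error. The model also leaves out relapse during the year.

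**The case against.** The strongest reply is that the amendment promises only associations. Its Data Analysis paragraph compares abstinent with non-abstinent participants without giving a direction, and a hospitalisation that precedes quitting is a legitimate correlate of abstinence. That stands as far as it goes: the planned calculation is not wrong as a cross-sectional description. It does not answer the concern, because the stated purpose concerns smoking cessation and the design is called prospective.

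Several stronger readings are tempting, and the documents do not support them.

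- *Smoking status at the time of an event cannot be reconstructed, and duration of abstinence cannot be obtained.* Methods lists topics, not the questionnaire. Objective 1 implies that some duration data are intended. What can be said is that the amendment does not state that quit dates or event dates will be collected, or used for objectives 2 and 3.
- *Every outcome in objectives 2 and 3 precedes the exposure.* Attitudes to vaccination and perceptions of HIV care are concurrent with the call, and the timing of HIV-related outcomes is not given. Illness-prompted quitting is also not an obvious mechanism for vaccination or routine HIV visits.
- *The associations will be reversed.* If quitting is 5% in both groups, a true 1.0 stays at 1.0 and a true 0.6 is only diluted. Even at 10% against 5%, with 20% abstinent at the start, 0.6 becomes 0.86 and stays below 1.
- *The parent trial's verified 6-month status is a ready replacement.* Recruitment was planned over 38 months (3.C.4.c), the trial closed in 2020, and the amendment dates from October 2021. That status may be years old when the one-year window opens.

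It is also fair to say that a prospective study can mean new contact with an existing cohort. For recalled outcomes the word still misleads.

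**Conclusion.** The concern holds for COVID-19 illness, emergency visits and hospitalisations in objectives 2 and 3. Exposure is recorded after these outcomes and no time ordering is planned, so illness-prompted quitting can bias the associations.

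The size cannot be established from the documents. Under the assumed rates, a true odds ratio of 0.6 appears anywhere from 0.66 (dilution only) to 1.89 (reversed), depending mainly on how many smokers quit after an event. Reversal is a possibility under some rates and is not shown to occur.

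The point does not extend to vaccination attitudes, perceptions of care, or HIV-related outcomes of unstated timing. The parent trial's sample size and primary analysis are not affected. The change is worth making before interviews begin, because dates that are not collected cannot be supplied by analysis later.

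**What to change.** 1. Make sure the interview records the date of the last cigarette and the date of each COVID-19 illness, hospitalisation and emergency visit. If the questionnaire already does so, say this in the amendment.
2. For these outcomes, classify smoking before the event or at the start of the one-year window. The start of the window is simpler, because participants without an event then have the same reference date. COVID-19 illness has no stated look-back, so it needs a defined starting date.
3. Use recalled quit dates as the main source. Use the parent trial's verified 6-month status as supporting or sensitivity information, because it may be out of date.
4. Report associations with current status only as a cross-sectional description.
5. Call these analyses retrospective or cross-sectional in place of prospective.
6. State the source and timing of the HIV-related outcomes, so that readers can see whether the same issue applies to them.

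The cost is a few extra items in a 15-20 minute interview, some rewording, and recall error in the dates.
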